2.3.4.3 Medical history

Medical history will be analyzed on the FAS.

The respective history of heart disease, stroke, diabetes, hyperlipidemia, hypertension, and fatty liver will be analyzed in categories of medical history, current medical condition, and none as follows:

- Past medical history: The disease is 'Present' and not 'Ongoing'
- Current medical condition: The disease is 'Present' and 'Ongoing'
- None: The disease is 'Absent'

The number and percentage of participants with each medical history will be presented by group and overall; statistical significance for differences between the groups will be tested by Chisquare test or Fisher's exact test.

Other medical history, including all medical history collected in the 'Other medical history' eCRF page, will be analyzed in categories of past medical history and current medical condition as follows:

- Past medical history: The disease is not 'Ongoing'
- Current medical condition: The disease is 'Ongoing'

For past medical history and current medical conditions, the number and percentage of participants with at least one medical history overall and in each SOC and PT of MedDRA will be presented by group and overall.

2.3.4.4 Medications

Medications will be analyzed on the FAS; prior and concomitant medications, including all medications collected in the 'prior/concomitant medications' eCRF page, will be analyzed in categories as follows:

- Prior medication: The medication is not 'Ongoing'
- Concomitant medication: The medication is 'Ongoing'

For prior and concomitant medications, the number and percentage of participants having at least one medication overall and in each WHO DD Therapeutic Main Group and Preferred Name will be presented by group and overall.

2.3.4.5 PsO related treatment other than medication

Prior/concomitant PsO related treatments other than medications will be analyzed for the FAS; prior and concomitant treatments, including all treatments collected in the 'Prior/concomitant PsO related treatments' eCRF page, will be analyzed in categories as follows:

- Prior PsO related treatment other than medication: The treatment is not 'Ongoing'
- Concomitant PsO related treatment other than medication: The treatment is 'Ongoing'

For prior and concomitant PsO related treatments, the number and percentage of participants with at least one treatment overall and in each SOC and PT of MedDRA will be presented by group and overall.

2.4 Analysis supporting primary objective(s)

The primary objective of this study is to compare the detection rate of PsA in patients with moderate-to-severe PsO between the EARP group and the Routine practice group.

2.4.1 Primary endpoint(s)

The primary endpoint of the study is the detection rate of PsA. Detection rate of PsA is defined as the percentage of subjects with true positive results divided by all subjects in each EARP or Routine practice group.

True positive results of PsA detection rate are defined as subjects with CASPAR score ≥ 3 among subjects with EARP ≥ 3 in the EARP group and among those suspected of PsA by investigator's judgment in the Routine Practice group.

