1.2 Purpose

Delays in diagnosis of PsA can lead to irreversible joint damage, therefore early detection of PsA through active screening of arthritis symptoms in PsO patients can be beneficial. The EARP is a simple and easy-to-use screening tool which can be utilized in a real-world setting of dermatology practice, and it is focused on early diagnosis of PsA. The purpose of this study is to confirm that the EARP screening is effective in early diagnosis of PsA.

2 Objectives and endpoints

The objectives of this study and the related endpoints are as follows.

Table 2-1 Objectives and related endpoints

Objective(s)	Endpoint(s)
Primary Objective(s)	Endpoint(s) for primary objective(s)

 To compare the detection rate of PsA with EARP screening versus detection rate of PsA without EARP screening in routine clinical practice in dermatological clinics amongst moderate to severe Korean PsO patients 	
 Detection rate of PsA
Secondary Objective(s)	Endpoint(s) for secondary objective(s)

 To compare the sensitivity, specificity, positive predictive value (PPV) and negative predictive value (NPV) between EARP questionnaire (EARP group) and the investigator's judgement (Routine practice group) To describe the patient characteristics and disease severity between PsA and non-PsA patients 	
 Sensitivity, specificity, PPV and NPV Description of demographic characteristics, medications and PsO related characteristics

Detection rate of PsA is defined as the percentage of the subjects with true positive results divided by all subjects in each EARP or Routine practice group ($=\text{TP}/(\text{TP}+\text{FP}+\text{TN}+\text{FN})$)

Sensitivity is defined as the percentage of the subjects with true positive results divided by CASPAR score ≥ 3 subjects in each EARP or Routine Practice group ($=\text{TP}/(\text{TP}+\text{FN})$)

Specificity is defined as the percentage of the subjects with true negative results divided by CASPAR score < 3 subjects in each EARP or Routine Practice group (=TN/(TN+FP))

PPV is defined as the percentage of the subjects with true positive results divided by EARP \geq 3 subjects in the EARP group and as the percentage of the subjects with true positive results divided by the subjects suspected of PsA by investigator's judgement in the Routine Practice group (=TP/(TP+FP))

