NPV is defined as the percentage of the subjects with true negative results divided by EARP < 3 subjects in the EARP group and as the percentage of the subjects with true negative results divided by the subjects not suspected of PSA by investigator's judgement in the Routine Practice group (=TN/(TN+FN))

The true positive results are defined as subjects with CASPAR score \geq 3 among EARP \geq 3 for the EARP group and among those suspected of PsA by investigator's judgement for the Routine Practice group.

The true negative results are defined as subjects with CASPAR score < 3 among EARP < 3 for the EARP group and among those not suspected of PsA by investigator's judgement for the Routine Practice group (Table 2-2).

Table 2-2 Evaluation outcomes

EARP group		
	CASPAR \geq 3 (positive)	CASPAR < 3 (negative)
EARP \geq 3 (positive)	TP (True Positive)	FP (False Positive)
EARP < 3 (negative)	FN (False Negative)	TN (True Negative)
Routine Practice group		
	CASPAR \geq 3 (positive)	CASPAR < 3 (negative)
Suspected of PsA by investigator's judgement (positive)	TP (True Positive)	FP (False Positive)
Not suspected of PsA by investigator's judgement (negative)	FN (False Negative)	TN (True Negative)

3 Study design

This is a randomized, open, parallel, controlled, multi-center, interventional, cross-sectional study to evaluate the detection rate of PsA in Korean moderate to severe PsO patients with or without the EARP screening.

[figure not shown]
All procedures for each patient will be performed for one day. If an additional time is required depending on the circumstances of the institution and so on, the data specified in this study protocol are recommended to be collected as soon as possible. After the participants are enrolled in this study, they will be assessed whether they meet the inclusion/exclusion criteria. In terms

of the severity of PsO, it will be assessed with the Psoriasis Area and Severity Index (PASI) and if the score of 10 or higher is defined as moderate to severe PsO. A total 368 eligible participants will be randomized 1:1 into the EARP group and the Routine practice groups.

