8.5.1 Primary endpoint

The primary endpoint of this study is detection rate of PsA. The assessments are measured by the CASPAR including clinical assessment, radiography and blood test. In addition, some values which are included the CASPAR are replaced by the values in Section 8.2.

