8.5.2 Secondary endpoint

The secondary endpoints of this study are as follows.

- Sensitivity, specificity, PPV and NPV
- Description of demographic characteristics, medications and PsO related characteristics

Sensitivity, specificity, PPV and NPV will use CASPAR to determine PsA diagnosis, and be compared between EARP questionnaire (EARP group) and the investigator's judgement (Routine practice group) (Section 8.5.1.1).

Description of demographic characteristics, medications and PsO related characteristics will be compared between PsA and non-PsA patients. Details of the variables are in Section 8.5.2.1 to 8.5.2.3 and the assessment will be measured by the values in Section 8.2 and 8.4.

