This Statistical Analysis Plan (SAP) is based on CAIN457AKR04 Protocol Version 1.0 dated 29Mar2022 and Case Report Form (CRF) Version 1.1 dated 08Jun2022 to provide a detailed description of the main features of the statistical analyses discussed in Section 12 of the Protocol, particularly, to present the endpoints and provide detailed information on the procedures and methods for their statistical analyses.

This SAP is to be finalized prior to data lock, and any changes made after its approval will be documented.

[figure not shown]

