The true negative results are defined as subjects with CASPAR score < 3 among subjects with EARP < 3 in the EARP group and among those not suspected of PsA by investigator's judgment in the Routine Practice group (Table II).

Table II Evaluation outcomes

Table II Evaluation outcomes				
EARP group				
	CASPAR ≥ 3 (positive)	CASPAR < 3 (negative)		
EARP ≥ 3 (positive)	TP (True Positive)	FP (False Positive)		
EARP < 3 (negative)	FN (False Negative)	TN (True Negative)		
Routine practice group				
	CASPAR ≥ 3 (positive)	CASPAR < 3 (negative)		
Suspected of PsA by investigator's judgment (positive)	TP (True Positive)	FP (False Positive)		
Not suspected of PsA by investigator's judgment (negative)	FN (False Negative)	TN (True Negative)		

2 Statistical methods

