2.5.2 Demographic characteristics and PsO related characteristics with or without PsA

Demographic and PsO related characteristics by the presence or absence of PsA will be analyzed on the FAS and PPS. The presence or absence of PsA is defined as below:

- PsA present: PsA diagnosis result is true positive
- PsA absent: PsA diagnosis result is false positive, true negative, or false negative

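### The outcome cells are defined by CASPAR score ≥ 3 alone, without the inflammatory articular disease condition that Protocol 8.5.1.1 requires

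*SAP*

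**What the plan says.** The protocol sets out the CASPAR rule in Section 1.1, Section 3 and Section 8.5.1.1 (Table 8-2). In each place PsA needs inflammatory articular disease (peripheral joint, entheseal or axial) and at least 3 points. Section 8.5.1 says of the primary endpoint: "The assessments are measured by the CASPAR including clinical assessment, radiography and blood test". Section 8.5.2 says: "Sensitivity, specificity, PPV and NPV will use CASPAR to determine PsA diagnosis", and points to 8.5.1.1.

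The definitions that produce the four cells do not carry the stem:

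- SAP 2.4.1: "True positive results of PsA detection rate are defined as subjects with CASPAR score ≥ 3 among subjects with EARP ≥ 3". Protocol 12.4.1 gives the same rule.
- Protocol Section 2, true negatives: "The true negative results are defined as subjects with CASPAR score < 3 among EARP < 3 for the EARP group". SAP 1.2 repeats it: "The true negative results are defined as subjects with CASPAR score < 3 among subjects with EARP < 3 in the EARP group".
- Protocol Section 2, sensitivity: "true positive results divided by CASPAR score ≥ 3 subjects in each EARP or Routine Practice group".
- Protocol Table 2-2 and SAP Table II label their columns only by score, at least 3 or below 3.

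SAP 1.1 does mention inflammatory articular disease, but as the name of a score that must reach 3, not as a separate condition. The SAP's stated aim is "to provide a detailed description of the main features of the statistical analyses discussed in Section 12 of the Protocol", and the SAP text available has no reference to Protocol 8.5.1.1.

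**The concern.** In this population the score hardly separates participants, so the stem does almost all of the diagnostic work. Dropping it moves most participants without PsA from the CASPAR-negative to the CASPAR-positive column.

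- **Primary endpoint.** Screen-positive participants without articular disease enter the numerator. The detection rate drifts toward the plain screen-positive rate, and an arm gains by flagging more people, rightly or wrongly.
- **Accuracy measures.** Screen-negative participants without articular disease become false negatives. Sensitivity and NPV collapse, PPV is inflated, and specificity rests on a handful of participants.
- **SAP 2.5.2.** The PsA-present group is the true positives, so it would include people with no articular disease. Screen-negative participants without articular disease stay in the other group ("PsA absent: PsA diagnosis result is false positive, true negative, or false negative"), which is the right place for them.

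**Working it through.** **The plan's own figure.** Protocol 12.7 and SAP 3 use 9% versus 19.7%, two-sided 0.05 and 80% power: (1.96 + 0.842)² × (0.09 × 0.91 + 0.197 × 0.803) / 0.107² = 164.64, so 165 per arm. Then 165 / 0.90 = 183.3, so 184 per arm and 368 in total. The figure reproduces, and the concern does not affect it.

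**Points.** Eligibility requires PASI ≥ 10, hence current psoriasis, 2 points. Negative RF adds 1, giving 3 with no articular disease. Family history, nail dystrophy, dactylitis or radiographic change each adds the same single point. Of the 2⁵ = 32 patterns of these five items, 31 reach 3. The exception is an RF-positive participant with none of the other four.

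**Inputs for size.**
- From the documents: 165 per arm; prevalence 13.76% or 19.7% (figures cited in the sample size section).
- Assumed, not in the documents: r, the share of participants without PsA who are RF-negative, 85–98%; sensitivity 65% in both arms, so no true difference; specificities 80–95%; all true PsA cases score at least 3; RF is the only route to the third point.

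**Formulas.**
- Detection rate as coded = prev × Se + (1 − prev) × (1 − Sp) × r
- Shift in the difference = (1 − prev) × (Sp routine − Sp EARP) × r
- TP′ = TP + r·FP; FN′ = FN + r·TN; FP′ = (1 − r)·FP; TN′ = (1 − r)·TN

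**One worked case** (prevalence 19.7%, r = 0.90, specificity 80% EARP, 95% routine). The correct rate is 0.197 × 0.65 = 12.8% in both arms. As coded:
- EARP: 0.128 + 0.803 × 0.20 × 0.90 = 27.3%
- Routine: 0.128 + 0.803 × 0.05 × 0.90 = 16.4%

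The difference is 10.8 points when the truth is zero. The design difference is 19.7 − 9 = 10.7.

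**Shift over the range.** It is 3.4–4.2 points per 5-point specificity gap and 10.2–12.7 per 15-point gap, in either direction.

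**Chance that superiority is claimed with no true difference** (lower limit of the unpooled 95% CI above 0, exact binomial enumeration, 165 per arm; 2.5% under the two-part rule):

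| EARP specificity | Routine specificity | As coded |
|---|---|---|
| 80% | 95% | 63–84% |
| 80% | 90% | 32–47% |
| 80% | 85% | 11–15% |
| 80% | 80% | 2.6% |
| 90% | 95% | 13–19% |
| 90% | 85% | 0.2–0.4% |
| 95% | 80% | under 0.1% |

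**Power when both arms flag the same share of participants without PsA.** The rates become 0.197 + q·f·r and 0.09 + q·f·r, where f is the share flagged and q the share without PsA. q runs from 1 − 0.197 = 0.803 (EARP sensitivity 100%) to 1 − 0.197/0.65 = 0.697 (EARP sensitivity 65%, which implies a prevalence of 30.3%). Power falls from 81% at f = 0 to 73–74% (f = 5%), 66–69% (10%), 57–61% (20%) and 52–56% (30%).

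**Accuracy measures** (specificity 80–95%):

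| Measure | Two-part rule | Score only |
|---|---|---|
| Sensitivity | 65% | 13–30% |
| PPV | 34–76% | 90–99.5% |
| NPV | 90–94% | 2–14% |
| CASPAR-negative per arm | 132–142 | 3–21 |

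Expected specificity is unchanged if RF is unrelated to the screen result; only its denominator shrinks.

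**The case against.** The best defence is that the score wording is shorthand for meeting CASPAR. The full rule is in the protocol, and Sections 8.5.1 and 8.5.2 tie the endpoints to it. The protocol summary counts PsA confirmed by the CASPAR criteria, 12.4.2 speaks of patients with PsA, and SAP 1.1 at least names inflammatory articular disease. The CRF, on which the SAP also rests, is not available here and may record the stem as a gate. A literal coding would also be conspicuous, with NPV of 2–14% in the same set of outputs, and it could be repaired because the stem items are collected. Finally, the size rests on assumed inputs.

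Much of this stands. The intent is very likely the two-part rule, the harm depends on how the derivation is programmed, and the figures fix neither size nor direction. With equal specificities the false-claim rate is about 2.6%, so the cost there is power. Treating RF as the only route to the third point is a simplification. Other routes would raise the share reaching 3 points, and specificity could change if those items are related to the screen result.

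None of it corrects the text. Protocol 12.4.1, the section that the SAP sets out to detail, uses the score alone, and so does every cell definition in the SAP. SAP Section 4 declares no change from the protocol. A programmer and an independent checker working from the SAP could agree on the same wrong derivation. Noticing the error in the outputs would mean redefining the primary endpoint after results are seen.

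**Conclusion.** The concern holds, and the text must be corrected. The operative definitions contradict the protocol's own CASPAR rule and, if followed, give a wrong primary endpoint and wrong accuracy measures. That part rests on the documents alone: 2 + 1 = 3 points without articular disease. The numerical consequences are illustrative and conditional on literal programming. Under the assumptions stated, the false-superiority rate runs from under 0.1% to 84%, and power at the planned rates falls from 81% to as low as 52%. Confidence is high in the contradiction; whether the derivation will in fact be coded this way cannot be judged from the documents.

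**What to change.** In SAP 1.2, Table II and 2.4.1, and in Protocol Section 2, Table 2-2 and 12.4.1, define the reference standard once and use it for all four cells and for the sensitivity and specificity denominators:

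- CASPAR-positive: meets CASPAR per Protocol 8.5.1.1, that is, inflammatory articular disease present and at least 3 points.
- CASPAR-negative: does not meet CASPAR, that is, stem absent or fewer than 3 points.

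Align the diagnostic sentence in SAP 1.1 with Protocol Section 3. The PsA-present group in SAP 2.5.2 is then corrected through the true positive definition. The cost is wording and derivation code. The stem items are already collected under Protocol 8.5.1.1, and the sample size and the test do not change.

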2.4.2 Statistical hypothesis, model, and method of analysis

To compare PsA detection rates between the EARP group and the Routine practice group, the following hypothesis will be tested at a two-sided 0.05 level.

$$H_0: P_I = P_C vs. H_a: P_I \neq P_C$$

where P_I and P_C are the detection rate of PsA in the EARP group and the Routine practice group, respectively.

English SAP Version 01 (release date: 15Jun2023)

The number of participants with true positive and the detection rate of PsA will be presented by each group using the FAS. The point-estimate of the difference in detection rate between the two groups (EARP group - Routine practice group) will be given with its two-sided 95% Confidence Interval (CI) and the p-value for the null hypothesis. If the lower limit of the twosided 95% CI of the difference between the two groups is greater than 0, the EARP group is deemed superior to the Routine practice group.

2.4.3 Supplementary analyses

The same analyses for the FAS will be conducted for the PPS for the primary efficacy endpoint, and the results will be presented.

2.5 Analysis supporting secondary objectives

2.5.1 Sensitivity, specificity, PPV and NPV

Analyses for sensitivity, specificity, PPV and NPV will be performed on the FAS and PPS.

Sensitivity will be summarized with the number and percentage of participants who have true positive (TP) among those who have true positive (TP) and false negative (FN), and the statistical significance of the difference between the two groups will be tested using Chi-square test or Fisher's exact test.

Specificity will be summarized with the number and percentage of participants who have true negative (TN) among those who have true negative (TN) and false positive (FP), and the statistical significance of the difference between the two groups will be tested using Chi-square test or Fisher's exact test.

Positive predictive value will be summarized with the number and percentage of participants who have true positive (TP) among those who have true positive (TP) and false positive (FP), and the statistical significance of the difference between the two groups will be tested using Chi-square test or Fisher's exact test.

Negative predictive value will be summarized with the number and percentage of participants who have true negative (TN) among those who have true negative (TN) and false negative (FN), and the statistical significance of the difference between the two groups will be tested using Chi-square test or Fisher's exact test.

2.5.2 Demographic characteristics and PsO related characteristics with or without PsA

Demographic and PsO related characteristics by the presence or absence of PsA will be analyzed on the FAS and PPS. The presence or absence of PsA is defined as below:

- PsA present: PsA diagnosis result is true positive
- PsA absent: PsA diagnosis result is false positive, true negative, or false negative

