For the EARP group, the investigator will ask the participants about the EARP questionnaire consisting of 10 questions. When the EARP score ≥ 3 , the participants will be suspected for having potential PsA. For Routine practice group, the investigator will select the participants suspected of PsA in consideration of the various clinical characteristics of the participants.

After the completion of EARP questionnaire evaluation and the investigator's judgement as per routine practice in each group, all the participants will be evaluated using CASPAR. According to the CASPAR, participants who have inflammatory articular disease with 3 or more points from the CASPAR are diagnosed as PsA, and the detection rate of PsA in each group is evaluated and compared.

Figure 3-1 Study design

4 Rationale

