	Smoking status	X			
Pregnancy tests ²⁾	X				
Inclusion/exclusion criteria	X				
Medical history and medication ³⁾	Medical history	X			
	PsO related medical history	X			
	Medications	X			
	PsO related treatment other than medications	X			
Randomization			X		
Intervention	EARP screening (EAPR group)			X	
	Investigator's judgement (Routine practice group)			X	
Physical examination	NAPSI				X
	SJC66				X
	TJC68				X

Period	Screening	Randomization	Intervention	Physical examination	Evaluation
Visit Name	Visit 1				
Day/Week/Month	Day 1				
CASPAR ⁴⁾	Clinical assessment				X
	Blood test				X
	Radiography				X

PsO; Psoriasis; EARp: Early arthritis for psoriatic patients; NAPSI: Nail psoriasis severity index; SJC: Swollen joint count; TJC: Tender joint count; CASPAR: Classification criteria for psoriatic arthritis; PsA: Psoriatic arthritis

- 1) All procedures must be conducted after getting ICF, and participant numbers are assigned in the order of consent.
- 2) For all female patients of child bearing potential only, a urine-HCG test will be performed.

3) Medical history and medication

- Medical history: Heart diseases, stroke, diabetes, hyperlipidemia, hypertension, fatty liver and other diseases
- PsO related medical history: Date of diagnosis for PsO, family history of PsO, family history of PsA, PASI score, hard-to-treat area involvement (scalp, palmoplantar and nails), musculoskeletal symptoms
- Medications
- PsO related treatment other than medications

4) CASPAR: Based on the CASPAR, participants are diagnosed with or without PsA.

- Clinical assessment: Inflammatory articular disease (inflammatory joint (peripheral) disease, enthesitis, and inflammatory axial disease), date of diagnosis for PsO#, family history of PsO#, presence or absence of typical psoriatic nail dystrophy (onycholysis, pitting, hyperkeratosis), presence or absence of dactylitis, history of dactylitis (recorded by rheumatologist)
- Blood test: Rheumatoid factor
- Radiography: Hand and foot plain X-ray (evidence of juxta-articular new bone formation in hand (including wrist) and feet (including ankle))

Note) #: These values which are included the CASPAR are replaced by the values in Section 8.2.2.2.

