8.5.1.1 CASPAR

In this study, the CASPAR will be measured for all participants after the EARP questionnaire evaluation and the investigator's judgement are completed in each group. The details of the CASPAR scoring are in the Table 8-2 (Cantini F, et al. 2010).

Table 8-2 CASPAR score

To meet the CASPAR, a patient must have an inflammatory articular disease (inflammatory joint (peripheral) disease, enthesitis, or inflammatory axial disease) with ≥ 3 points from the above criteria.

Criteria	Point
Current PsO	2
Personal history of PsO	1

To meet the CASPAR, a patient must have an inflammatory articular disease (inflammatory joint (peripheral) disease, enthesitis, or inflammatory axial disease) with ≥ 3 points from the above criteria.

Criteria	Point
Family history of PsO	1
Typical PsO nail dystrophy (onycholysis, pitting, hyperkeratosis)	1
Current dactylitis or history of dactylitis	1
Negative rheumatoid factor	1
Hand and foot plain radiography (evidence of juxta-articular new bone formation in hand (including wrist) and feet (including ankle))	1

The items for the CASPAR measurement are as follows.

- Clinical assessment

Inflammatory joint disease (presence or absence of Inflammatory joint (peripheral) disease, enthesitis and inflammatory axial disease), date of diagnosis for PsO[#], family history of PsO[#], presence or absence of typical psoriatic nail dystrophy (onycholysis, pitting, hyperkeratosis), presence or absence of dactylitis, history of dactylitis
- Blood test

Rheumatoid factor
- Radiography

Hand and foot plain X-ray (evidence of juxta-articular new bone formation in hand (including wrist) and feet (including ankle))

Note) #: These values which are included the CASPAR are replaced by the values in Section 8.2.2.2.

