1.2 Study objectives and endpoints

The objectives of this study and the related endpoints are as follows.

Table I Objectives and related endpoints

Objective(s)	Endpoint(s)	
Primary objective(s) To compare the detection rate of PsA with EARP screening versus detection rate of PsA without EARP screening in routine clinical practice in dermatological clinics amongst moderate to severe Korean PsO patients	Endpoint(s) for the primary objective(s)Detection rate of PsA	
Secondary objective(s)	Endpoint(s) for the secondary objective(s)	
 To compare the sensitivity, specificity, positive predictive value (PPV) and negative predictive value (NPV) between EARP questionnaire (EARP group) and the investigator's judgment (Routine practice group) 	Sensitivity, specificity, PPV and NPV	
 To describe the patient characteristics and disease severity between PsA and non-PsA patients 	 Description of demographic characteristics, medications and PsO related characteristics 	

Detection rate of PsA is defined as the percentage of subjects with true positive results divided by all subjects in each EARP or Routine practice group (=TP/(TP+FP+TN+FN))

Sensitivity is defined as the percentage of subjects with true positive results divided by CASPAR score ≥ 3 subjects in each EARP or Routine Practice group (=TP/(TP+FN))

Specificity is defined as the percentage of subjects with true negative results divided by CASPAR score < 3 subjects in each EARP or Routine Practice group (=TN/(TN+FP))

PPV is defined as the percentage of subjects with true positive results divided by EARP \geq 3 subjects in the EARP group and as the percentage of subjects with true positive results divided by subjects suspected of PsA by investigator's judgment in the Routine Practice group (=TP/(TP+FP))

NPV is defined as the percentage of subjects with true negative results divided by EARP < 3 subjects in the EARP group and as the percentage of subjects with true negative results divided by subjects not suspected of PSA by investigator's judgment in the Routine Practice group (=TN/(TN+FN))

True positive results are defined as subjects with CASPAR score ≥ 3 among subjects with EARP ≥ 3 in the EARP group and among those suspected of PsA by investigator's judgment in the Routine Practice group.

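### SAP 2.5.2 counts false negatives, who meet CASPAR, as PsA absent, so the PsA versus non-PsA tables compare detected with not-detected patients

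*SAP*

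**What the plan says.** **Objective.** Protocol Section 2 (Table 2-1) and SAP 1.2 give the second secondary objective as "To describe the patient characteristics and disease severity between PsA and non-PsA patients". Protocol 12.5.2 presents these tables by patients with and without PsA. It contains no rule restricting PsA to screen-detected cases.

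**How PsA is diagnosed.** Protocol Section 3 states that "participants who have inflammatory articular disease with 3 or more points from the CASPAR are diagnosed as PsA". Footnote 4 of Protocol Table 8-1 says "Based on the CASPAR, participants are diagnosed with or without PsA". Under Protocol 8.5.1.1, "the CASPAR will be measured for all participants after the EARP questionnaire evaluation" and the investigator's judgement, so CASPAR status is known whatever the screen result. Protocol 8.5.2 adds: "Sensitivity, specificity, PPV and NPV will use CASPAR to determine PsA diagnosis".

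**The 2×2 cells.** Protocol Table 2-2 and SAP Table II place false negatives in the CASPAR-positive column. SAP 1.2 defines sensitivity as true positives "divided by CASPAR score ≥ 3 subjects in each EARP or Routine Practice group (=TP/(TP+FN)).

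**The grouping rule.** SAP 2.5.2 defines *PsA present* as a true positive result only. The complement reads: "PsA absent: PsA diagnosis result is false positive, true negative, or false negative". SAP Section 4 declares no departures from the protocol's analyses.

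**The concern.** A false negative has PsA in SAP 2.5.1, where it counts in the sensitivity denominator, and has no PsA in SAP 2.5.2. True positives against everyone else is a comparison of detected with not-detected patients, which is a different question from the stated objective.

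The rule governs demographics, PsO characteristics, medical history, medications and other treatments, on both FAS and PPS, with p-values in SAP 2.5.2.1 to 2.5.2.3. A reader would take the column headings at face value.

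Two consequences follow.

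- If the arms detect at different rates, which is the trial's hypothesis, being in the *present* group partly reflects randomised arm.
- Entry to the *present* group requires a positive screen. EARP asks about joint symptoms (Protocol 8.3), and routine judgement may include a question on joint pain (Protocol 6.1.2). Musculoskeletal symptoms and joint counts are among the characteristics compared, so the grouping selects on related information.

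The direction of any bias is unknown, because the documents do not say how missed cases differ from detected ones.

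A possible source is Protocol 12.4.2, which describes the tested proportion as that of patients with PsA, although 12.4.1 defines it as true positives over all patients. PsA is thus used in two senses.

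**Working it through.** **1. Cell membership**

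| Cell | Screen | CASPAR | Has PsA (Protocol 3, Table 8-1) | SAP 2.5.2 label |
|---|---|---|---|---|
| TP | + | + | yes | present |
| FN | − | + | yes | **absent** |
| FP | + | − | no | absent |
| TN | − | − | no | absent |

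Only the FN row conflicts.

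**2. Inputs** (Protocol 12.7, SAP 3): detection rates, defined as TP over all patients, of 19.7% for EARP and 9% for Routine practice; 1:1 allocation. The planned size reproduces: (1.96 + 0.842)² × (0.09×0.91 + 0.197×0.803) / 0.107² = 164.64, so 165 per arm; 165/0.9 gives 184. I use 165 evaluable per arm. The percentages in steps 3 and 4 do not depend on this number.

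**3. Composition of *PsA present* at the planned rates**

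- EARP TP = 165 × 0.197 = 32.5; Routine TP = 165 × 0.09 = 14.85; total 47.4.
- EARP share = 32.5/47.4 = 69%; Routine share = 31%.
- *PsA absent* = 330 − 47.4 = 282.6.

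A CASPAR-based group would be expected to split about 50/50, provided CASPAR is ascertained alike in both arms.

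**4. PsA cases labelled absent.** With prevalence π equal in the two arms, FN = 330π − TP. The plan gives neither π for this trial nor a sensitivity (Se) for EARP, so π and Se below are assumptions.

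| Assumption | π | PsA cases | TP | FN | FN / PsA cases | FN / *absent* |
|---|---|---|---|---|---|---|
| A: planned rates, EARP Se 1 | 19.7% | 65.0 | 47.4 | 17.7 | 27% | 6.2% |
| B: planned rates, EARP Se 0.9 | 0.197/0.9 = 21.9% | 72.2 | 47.4 | 24.9 | 34% | 8.8% |
| B: planned rates, EARP Se 0.8 | 0.197/0.8 = 24.6% | 81.3 | 47.4 | 33.9 | 42% | 12.0% |
| B: planned rates, EARP Se 0.7 | 0.197/0.7 = 28.1% | 92.9 | 47.4 | 45.5 | 49% | 16.1% |
| C: Routine 9%, EARP Se 1, low end of Korean range | 9% | 29.7 | 29.7 | 0 | 0% | 0% |
| C: Routine 9%, EARP Se 1, high end of Korean range | 14.1% | 46.5 | 165 × (0.141 + 0.09) = 38.1 | 8.4 | 18% | 2.9% |

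Under A, π is the lowest value compatible with the planned EARP rate, and all 17.7 false negatives are in the Routine arm. Assumption C gives up the planned EARP rate. The EARP share of *present* is then 0.09/0.18 = 50% at the low end and 0.141/0.231 = 61% at the high end, against 69% at the planned rates.

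**5. Why the articular requirement must be stated.** Protocol Table 8-2 says "a patient must have an inflammatory articular disease (inflammatory joint (peripheral) disease, enthesitis, or inflammatory axial disease) with" at least 3 points. Current PsO scores 2 and a negative rheumatoid factor scores 1, so 2 + 1 = 3 is reached with no joint disease. Table II shows only the score, and SAP 1.1 words the rule as a score for inflammatory articular disease. A redefinition by score alone would be wrong in the other direction.

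**The case against.** **The rule may be deliberate.** It is printed in full, and the protocol leaves technical details to the SAP. Protocol 12.4.2 also uses PsA loosely for the true-positive proportion. This makes the rule transparent but not correct: relabelling the tables would make them honest and still leave the objective unanswered. Protocol 12.4.2 concerns the primary hypothesis, and SAP 2.4.2 itself words that proportion as a detection rate.

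**The consequence is limited.** This stands. The tables are descriptive, FN counts can be recovered from the sensitivity and NPV tables, and the data can be regrouped at any time.

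**The size rests on assumption.** This stands in part. The share of cases labelled absent runs from 0% to 49%, the sensitivities in B appear nowhere in the documents, and the 69% split holds only at the planned rates. The misclassification itself follows from the definitions and needs no assumption.

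**An even split is conditional.** This stands. Protocol 6.3 leaves the assigned group open to those performing the assessments, so CASPAR ascertainment could differ by arm.

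**The articular wording reaches further.** Writing it into Table II touches the cells used for the primary endpoint and the accuracy measures. It does, but it only states what Protocol Section 3 and Table 8-2 already require. Changing Protocol 12.4.2, by contrast, would need an amendment under Protocol 14.1.

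**Conclusion.** The concern holds. SAP 2.5.2 contradicts the documents' own 2×2 table and the protocol's CASPAR-based diagnosis, and nothing elsewhere corrects it. The tables in SAP 2.5.2.1 to 2.5.2.5 would not deliver the second secondary objective.

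At the planned detection rates, 69% of the *present* group would come from one arm. About 27% of PsA cases would be labelled absent at an assumed prevalence of 19.7% with EARP missing nobody. The share is larger if EARP misses cases while keeping its planned detection rate, and between 0% and 18% if prevalence lies in the Korean range the plan cites.

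This should be fixed, but the damage is confined to one descriptive secondary objective. The grouping does not enter the primary endpoint, sensitivity, specificity, PPV, NPV or sample size.

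**What to change.** In SAP 2.5.2:

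- Define *PsA present* as meeting CASPAR, that is, inflammatory articular disease plus at least 3 points, whatever the screen result (TP + FN).
- Define *PsA absent* as not meeting CASPAR (FP + TN).
- State that the CASPAR columns of Table II are read the same way, and bring the wording in SAP 1.1 into line.
- If detected versus missed cases are of interest, show TP against FN in a separate table labelled as such.

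The use of PsA in Protocol 12.4.2 should be made consistent with 12.4.1 by amendment. The core fix does not depend on that step.

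The cost is a few lines of SAP text and regrouped output tables. No new data are needed, because CASPAR is measured in all participants. If the SAP is already approved, record the change as its introduction requires.
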